#### Inter-reader variability

Inter-reader variability will be evaluated on the whole set of study patients, since each case was read by 3 different readers.

Inter-reader variability will be presented using data from gadopiclenol period on FAS1 on the one hand and using paired images from gadopiclenol and gadobutrol on FAS2 on the other hand.

The same methodology as the one presented above for intra-off-site variability will be applied. One scatter plot for each of the 3 comparisons will be presented. The factor “reader” will be used instead of the factor “reading” in the model.

Presentation of patients and lesions.

Number of patients and lesions by contrast agents and MRI modalities for all efficacy datasets will be displayed using All Randomized Set.

#### Global model

The primary analysis 2 will be repeated with only one model including the reader as covariate using the FAS2. The results will be presented overall.

#### Non-matching lesions

The primary analyses1 and 2 will be repeated including the non-matching lesions using the Extended FAS1 and extended FAS2 respectively.

## Dropout patients

If the number of patients dropping out is different between series, then the primary analysis 2 will be repeated using All Randomized Set considering in the model as well, the patients having discontinued between period 1 and period 2. As the discontinued patients do not have matching lesion by definition, the analysis will take into account all lesions including the not matching ones.

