### 3. STATISTICAL METHODS

#### 3.1. General considerations

With regards to the ICH topic E9 addendum, it has been decided to not use the wording estimand. Indeed, the protocol was drafted in 2018 when the addendum was not yet adopted by competent authorities (CA). Nevertheless, for this diagnostic cross-over study, all analyses and presentation asked by CA in this addendum were considered and put in place if needed. Hence, no strategy for dealing with intercurrent event is considered. However, sensitivity analyses are planned in order to assess the robustness of the primary analysis. As it is expected that very few patients dropped-out because of results of diagnostic of first period but rather for safety or technical reasons, no specific missing data handling is planned. However, a sensitivity analysis accounting for discontinued patient is planned (in the mixed models).

After the database lock, the statistical analysis will be performed by a Contract Research Organization ██████████ under the supervision of Guerbet biostatistician, on the basis of the present document.

A quality control of the statistical analysis will be performed by the CRO to ensure the reliability of the results prior to providing the results to Guerbet.

Some analyses will be presented by series (gadopiclenol-gadobutrol / gadobutrol- gadopiclenol), especially those about demographic and baseline characteristics. Some analyses will be presented by MR modality (pre /paired) and some by contrast agent group (gadopiclenol / gadobutrol), especially those in efficacy and safety. For the presentation by contrast agent group, efficacy analyses will be presented as randomized, that is to say presented by allocated contrast media whereas safety analyses will be presented by actually administered contrast media.

Tabulations of quantitative parameters will include the following summary statistics: Number of Patients / Mean / Standard Deviation / Minimum / Median / Maximum. If for a given parameter, the raw value has been collected with x decimal places, the mean, median and standard deviation will be rounded to x+1 decimal places, while the minimum and maximum values will be tabulated as reported with x decimal places.

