### 3.5. Handling of dropouts or missing data

### 3.5.1. Efficacy Analyses

No imputation will be performed in this study. Mixed models will be performed only on patients with both MRIs for primary analyses.

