Further, the subgroup analysis by organ will include only following organs (Breast, Liver, Kidney, Pancreas, Prostate and those with more than 10% of patients for at least one reader). Patients with lesions in more than one organ will not be kept in the analysis.

In addition, if the number of patients dropping out is different between series, non-inferiority analysis will be repeated on all patients having at least one MRI performed.

Analysis of secondary criterion: patient's treatment plan will be augmented by presenting the results according to the nature (non malignant/malignant/not assessable) of the diagnosis done at unenhanced MRI and by adding therapeutic management based on unenhanced MRI

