### 5.2. Data Sets Analysed and protocol deviations

#### Data sets analysed

There will be nine patient sets defined for this trial: the Screened patients Set (SPS), the Safety Set (SS), the All Randomized Set (ARS), the Extended Full Analysis Set 1 & 2, the Full Analysis Set (FAS) 1 & 2 and the Per-Protocol Set (PPS) 1 & 2:

- Screened Patients Set (SPS) will include all patients having signed the inform consent form
- Safety Set (SS) will include all patients having received at least one injection of Investigational Medicinal Product (IMP) regardless of the quantity
- All Randomized Set (ARS) will include all patients having performed at least one MRI exam.
- Extended\_FAS1 will include all patients who have both gadopiclenol pre contrast and paired images assessable
- Extended FAS2 will include all patients who have both gadopiclenol and gadobutrol paired images assessable
- Full Analysis Set (FAS) will include all patients who have a valid primary criterion assessment
  - FAS1 will include all patients who have both gadopiclenol pre contrast and paired images assessable for primary criteria 1 for at least one matching lesion for at least one off-site reader
  - FAS2 will include all patients who have both gadopiclenol and gadobutrol paired images assessable for primary criteria 2 for at least one matching lesion for at least one off-site reader
- Per-Protocol Set (PPS) will include all patients who have no major protocol deviations and a valid primary criterion assessment:
  - PPS1 will include all patients from the FAS1 who have no major protocol deviations for primary criteria 1

- o PPS2 will include all patients from the FAS2 who have no major protocol deviations for primary criteria 2

Analyses Sets	Safety Set	All Randomized Set	Extended Full Analysis Set		Full Analysis Set		Per Protocol Set	
			Extended FAS1	Extended FAS2	FAS1	FAS2	PPS1	PPS2
Demographics and Population characteristics	✓				✓	✓		
Compliance					✓	✓		
Efficacy evaluation : primary analysis of primary criteria 1					✓		✓	
Efficacy evaluation : primary analysis of primary criteria 2						✓		✓
Efficacy evaluation: secondary analysis of primary criteria 1			✓		✓			
Efficacy evaluation: secondary analysis of primary criteria 2		✓		✓		✓		
Efficacy evaluation: Secondary criteria		✓	✓	✓	✓	✓		
Safety evaluation	✓							

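### The only objective 2 analysis that keeps patients who left after the first MRI depends on drop-out counts differing between series; counts are the wrong trigger, and the SAP elsewhere presents the analysis as planned.

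*SAP*

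**What the plan says.** SAP 3.1 expects few patients to leave because of the first-period diagnostic result, "rather for safety or technical reasons, no specific missing data handling is planned". It then adds: "However, a sensitivity analysis accounting for discontinued patient is planned (in the mixed models". No condition is attached there.

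SAP 4 and SAP 5.6.2 attach one. SAP 4 says that "if the number of patients dropping out is different between series, non-inferiority analysis will be repeated on all patients having at least one MRI performed". SAP 5.6.2 says: "If the number of patients dropping out is different between series, then the primary analysis 2 will be repeated using All Randomized Set". It adds that all lesions, matching or not, will be used. Neither section says what size of difference, or which test, makes the numbers *different*.

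The table list in SAP 6.1.2.1 includes Tables 14.2.1.32 and 14.2.1.33 for drop-out patients without a condition.

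The other sets used for objective 2 all need both examinations. SAP 3.5.1 rules out imputation and says "Mixed models will be performed only on patients with both MRIs for primary analyses". SAP 5.2 says "FAS2 will include all patients who have both gadopiclenol and gadobutrol paired images assessable for primary criteria 2", and PPS2 is drawn from FAS2. It also says "Extended FAS2 will include all patients who have both gadopiclenol and gadobutrol paired images assessable".

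**The concern.** In a two-period cross-over, a patient who has only the first MRI contributes no within-patient difference and is lost from a complete-pair analysis. Whether that loss biases the gadopiclenol minus gadobutrol estimate depends on who leaves after which agent. Equal numbers can leave both series while the reasons, and the first-period scores, of those leaving differ. The condition would then switch off the only model able to show the effect.

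The undefined word is a second weakness. Read literally, a difference of one patient is enough. Any softer reading is a judgement made with drop-out counts by series in view. The robustness check that SAP 3.1 presents as planned would then depend on how one word is read.

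**Working it through.** **Plan's own figure.** Inputs from SAP 3.3: margin 0.35 (used as -0.35), SD of the difference 1.75, true difference 0, 80% power, two-sided 95% CI.

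- n = (1.75 × (1.960 + 0.842) / 0.35)² = 14.01², which rounds up to 197. The noncentral t gives 199, and power at 200 is 80.4%. The stated 200 evaluable patients is reproduced and is not in dispute.

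**Is it the only objective 2 model that keeps one-MRI patients?** The primary and supportive analyses use PPS2 and FAS2. The global model and the subgroup models use FAS2. The non-matching-lesion run uses Extended FAS2. The readers regrouped for balance (Tables 14.2.1.35 and 14.2.1.37) use PPS2 and FAS2. The lesion-level models use FAS2 in the SAP text and Extended FAS2 in the table list. All need both examinations. The All Randomized Set needs only one MRI, but its other uses (technical adequacy, counts of patients and lesions, descriptive tables) do not test objective 2.

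**How often is the analysis skipped?** SAP 4 gives 25 drop-outs among 245 enrolled: 25/245 = 10.2%. Take 150 patients per series, each dropping out independently.

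- Literal reading (skipped only if counts are equal): the sum over k of P(k)², with P binomial (150, 0.102), is 7.6%. The analysis therefore runs about 92% of the time. For drop-out of 5% to 15%, a tie occurs 10.6% to 6.5% of the time. An odd total, such as 25, cannot tie.
- *Different* read as Fisher p < 0.05: the analysis runs 3.3% of the time when true rates are equal.

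**Can equal counts hide bias?** Assume 10% leave each series. In one series they are the highest first-MRI scorers; in the other they are a random 10%. Let s be the SD of a patient's score and r the within-patient correlation.

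- The mean of the top 10% of a normal distribution is 1.755 s above the overall mean, so those remaining sit 1.755 × 0.1/0.9 = 0.195 s below it.
- Their second score falls by r × 0.195 s, so the difference in that series shifts by 0.195 s (1 - r).
- Averaged over the two series: bias = 0.0975 s (1 - r).

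The score SDs 0.5 to 0.8 come from the SAP's phase IIb range; r of 0 to 0.5 is assumed.

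| s | r | Bias (points) | Share of 0.35 |
|---|---|---|---|
| 0.5 | 0.5 | 0.024 | 7% |
| 0.5 | 0 | 0.049 | 14% |
| 0.8 | 0.5 | 0.039 | 11% |
| 0.8 | 0 | 0.078 | 22% |

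If the gadopiclenol-first series loses its high scorers, the bias is against gadopiclenol. If the gadobutrol-first series does, it favours gadopiclenol. In simulations with equal counts, random drop-out, or the same mechanism in both series, gave no bias. Under selective drop-out, a compound-symmetry mixed model that kept one-MRI patients had a bias of at most 0.01.

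**Against the room to the margin.** With 200 pairs and a true difference of 0, the CI half-width is 1.972 × SD of difference / √200, where SD of difference = s√(2(1 - r)).

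- s = 0.5, r = 0.5: SD 0.50, half-width 0.07, room 0.28. The bias of 0.024 uses about 9%.
- s = 0.8, r = 0: SD 1.13, half-width 0.16, room 0.19. The bias of 0.078 uses about 41%.
- At the planning SD of 1.75 the half-width is 0.244 and the room 0.106. The same mechanism with r = 0 gives 0.0975 × 1.75/√2 = 0.121, slightly more than the room.

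**The case against.** The strongest reply is that the analysis will very probably run. As written, unequal means unequal, and the counts tie less than one time in ten. SAP 3.1 and the table list both treat the run as expected. SAP 5.1 already reports reasons for premature discontinuation by series (Table 14.1.1.4), so equal counts with different reasons would be visible, though not modelled. Patients do not leave because of the blinded off-site score, so selection can act only indirectly. At least 6 of the 25 drop-outs were due to Covid-19. All of this stands. It limits the size of the point but does not defend the condition: if the analysis nearly always runs, the clause serves no purpose, and if it does not, SAP 3.1 is not honoured.

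A reader might infer three stronger things that the documents do not support:

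- *That SAP 3.1 rests its lack of missing-data handling on this sensitivity analysis.* Its main reason is the expectation that drop-out will be for safety or technical reasons; the sensitivity analysis is an addition.
- *That 10.2% of patients left after the first MRI.* SAP 4 does not say when the 25 left, so 10.2% is an upper figure for that group.
- *That drop-out could by itself overturn the objective 2 conclusion.* The decision rule uses PPS2, which this supportive analysis does not enter. At the SDs the SAP derives from phase IIb, the illustrated bias stays inside the room to the margin. It exceeds the room only at 1.75, which the plan sets above its own expected range of 0.7 to 1.15 to allow for heterogeneity.

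**Conclusion.** The point holds as an inconsistency and a wrong trigger on a supportive analysis. SAP 4 and 5.6.2 impose a condition that SAP 3.1 and the table list lack. It governs the only objective 2 model that keeps patients who left after the first MRI. It tests how many leave, when bias comes from which patients leave after which agent. Because *different* is undefined, the chance of skipping the analysis ranges from about 8% (literal) to about 97% (significance test, equal true rates).

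The bias of 0.02 to 0.08 points is an illustration. It rests on an assumed mechanism acting in one series only, an assumed correlation of 0 to 0.5 and phase IIb SDs, and its direction depends on the series. On those assumptions it would not alone change the PPS2 decision. This is a free improvement rather than a threat to the trial's conclusion.

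**What to change.** Delete the condition in SAP 4 and SAP 5.6.2, so that both agree with SAP 3.1 and the table list. Suggested wording: *Primary analysis 2 will be repeated on the All Randomized Set, including patients who discontinued between period 1 and period 2, whatever the number of drop-outs in each series.*

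Read the result beside two outputs already planned. The first is the Extended FAS2 run (Table 14.2.1.30), which also uses all lesions, so that the effect of keeping drop-outs is separated from the effect of adding non-matching lesions. The second is the discontinuation reasons by series (Table 14.1.1.4).

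The cost is one deleted clause in each of two sections. Tables 14.2.1.32 and 14.2.1.33 are already listed, and neither the sample size nor the decision rule changes.

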### Check of normality assessment

Normal Probability Plot where the ranked residual values are plotted against the normal scores will be displayed for the two primary analyses.

### Analysis of secondary criteria

All analyses of the secondary criteria will be done using the extended FAS1 and extended FAS2 except otherwise specified. Tables using extended FAS 1 will include only data from the MRI using gadopiclone .

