- 3 = Injection technical failure
- 4 = Inadequate anatomic coverage
- 5 = Other, specify

7.2.6 ***Number, size and location of lesions (on-site and off-site read)***

The investigator and IBR is to record the following:

- Number of lesions on pre and paired images
- For the most 3 representative lesions, the following will be recorded for each lesion separately:
 - The largest diameter of the lesion
 - The location of the lesion
- In case that more than 3 lesions are present, the investigator/IBR has to enter in the eCRF how many lesions are present (total number).

 CONFIDENTIAL	Protocol No. GDX-44-011 Version No. 3.0 (including amendment 2) June 30, 2020	Page 41 / 82
---	---	--------------

7.2.7 ***Diagnostic confidence (on-site and off-site read)***

The investigator/IBR will record in the eCRF his/her diagnosis and his/her confidence in diagnosis for each patient for each pre and paired images of each contrast agent according to the following diagnosis:

- 1 = Negative
- 2 = Benign
- 3 = Probably Benign finding
- 4A = Low Suspicion of Malignancy
- 4B = Intermediate Suspicion of Malignancy
- 4C = Moderately High Suspicion of Malignancy
- 5 = Not assessable

If malignancy is diagnosed, then whether the tumor is primary or secondary should be specified.

Diagnostic confidence will be evaluated to determine the level of certainty that the investigator/IBR assign to a diagnosis. This is defined as the degree of confidence that the information on the images represents the true and complete clinical picture of a patient.

The degree of confidence will be rated on a 5-point scale:

- 1 = Nil: very uncertain
- 2 = Poor: uncertain
- 3 = Moderate: moderately certain
- 4 = High: good certainty
- 5 = Excellent: very certain

When the investigator/IBR chooses 'not assessable' for diagnosis, by definition the confidence level is 1 (= very uncertain).

7.2.8 ***Impact of contrast-enhanced MRI on patient treatment plan (on site)***

The impact on patient treatment plan will be assessed by on-site radiologists and will be summarized for each contrast agent. At the end of visit 2 and at the end of visit 4, after having completed all the sequences of images required by the protocol (images set 1b or set 2b), the investigator will have to document if the patient treatment plan could have been changed based on the images obtained (yes/no) and if yes, he/she would have to specify the therapeutic management proposed based on radiological assessment:

- Surgery
- Biopsy

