## Technical adequacy of images

The quality of images will be assessed by off-site readers and on-site radiologists. Technical adequacy and assessable status of images and will be tabulated by contrast agent groups and MRI modalities (pre and paired) using All Randomized Set; off-site and on-site reader's outcomes will be separately analyzed. Non assessable reasons will be only listed.

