#### Diagnostic confidence

The diagnosis for the patient and level of diagnostic confidence according to off-site readers and on-site radiologists will be displayed by contrast agent groups and MRI modalities (pre and paired); off-site and on-site reader's outcomes will be separately analyzed.

Level of diagnostic confidence will be summarized qualitatively and quantitatively by contrast agent groups and MRI modalities (pre and paired); off-site and on-site reader's outcomes will be separately analyzed.

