### Level of Diagnostic Confidence

Table 14.2.2.46	Radiological Diagnosis and Level of Diagnostic Confidence - Off-Site Readings - MRI with Gadopiclenol - Extended FAS 1
Table 14.2.2.47	Radiological Diagnosis and Level of Diagnostic Confidence - Off-Site Readings - MRI with Gadopiclenol vs MRI with Gadobutrol – Extended FAS 2
Table 14.2.2.48	Radiological Diagnosis and Level of Diagnostic Confidence - On-Site Reading – MRI with Gadopiclenol - Extended FAS 1
Table 14.2.2.49	Radiological Diagnosis and Level of Diagnostic Confidence - On-Site Reading – MRI with Gadopiclenol vs MRI with Gadobutrol – Extended FAS 2

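### Diagnostic confidence is tabulated only where images were assessable, so failed examinations recorded at the lowest confidence can drop out of the tables

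*SAP*

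**What the plan says.** SAP 5.6.2 (Analysis of secondary criteria) sets the default: "All analyses of the secondary criteria will be done using the extended FAS1 and extended FAS2 except otherwise specified". The diagnostic confidence paragraph names no other set and plans description only: "Level of diagnostic confidence will be summarized qualitatively and quantitatively by contrast agent groups and MRI modalities (pre and paired"). The four tables listed in SAP 6.1.2.2, 14.2.2.46 to 14.2.2.49, follow the default; the first is titled "Radiological Diagnosis and Level of Diagnostic Confidence - Off-Site Readings - MRI with Gadopiclenol - Extended FAS 1".

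Both sets are defined in SAP 5.2 by assessability. Extended FAS1 "will include all patients who have both gadopiclenol pre contrast and paired images assessable". For the agent comparison, "Extended FAS2 will include all patients who have both gadopiclenol and gadobutrol paired images assessable". Neither definition says whose judgement of assessability counts. FAS1 and FAS2, by contrast, need assessable images "for at least one matching lesion for at least one off-site reader".

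Protocol 7.2.7 asks for a diagnosis and a confidence score on each Pre and Paired image set of each agent, and fixes one score by rule: "When the investigator/IBR chooses 'not assessable' for diagnosis, by definition the confidence level is 1 (= very uncertain"). SAP 2.2.2 keeps 'not assessable' as a diagnosis but does not repeat the rule. Image assessability is a separate yes/no item with its own reasons (Protocol 7.2.5).

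For technical adequacy the SAP departs from the default: "Technical adequacy and assessable status of images and will be tabulated by contrast agent groups and MRI modalities (pre and paired) using All Randomized Set". That set holds all patients with at least one MRI performed.

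**The concern.** The stated objective is to assess diagnostic confidence with each agent. The planned tables describe confidence among patients whose relevant image sets were all assessable. An examination that failed is likely to be one on which the reader had little or no confidence, so membership of the analysis set is tied to the outcome it summarises.

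The exclusion is also made by patient. If the gadopiclenol Pre set fails, the usable Paired set leaves Extended FAS1 with it. If one agent's Paired set fails, the other agent's usable set leaves Extended FAS2. Mean confidence and the percentages at high confidence then describe examinations that worked, which is narrower than the objective.

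**Working it through.** **Inputs.** The documents give no figure for expected diagnostic confidence and none for the rate of non-assessable images, so there is no planned figure to reproduce. The nearest number is the estimate of about 68 patients without a valid primary criterion among 245 enrolled (SAP section 4), 68/245 = 27.8%. It cannot serve as a failure rate, because it also counts patients who only lack a matching lesion, and they stay in the Extended sets. The shares and means below are assumptions.

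**Effect on a single mean.** For one image type, let f be the share of reads that would carry a recorded score of 1 and are removed, and m the mean of the reads kept. Assume that usable sets lost with a failed partner would also average m.

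- Mean over all reads = (1 − f) × m + f × 1
- Overstatement = m − [(1 − f) × m + f] = f × (m − 1), never negative on a scale that starts at 1

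| f | overstatement, m = 3 | m = 4 | m = 4.5 |
|---|---|---|---|
| 1% | 0.02 | 0.03 | 0.035 |
| 5% | 0.10 | 0.15 | 0.175 |
| 10% | 0.20 | 0.30 | 0.35 |

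For example, with m = 4 and f = 5%: 0.95 × 4 + 0.05 = 3.85, against 4.00 in the restricted table.

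**Effect on the agent difference.** Take retained means of 4 for both agents, so the restricted difference is 0.

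- Agent A fails in 2%, agent B in 5%: (0.98 × 4 + 0.02) − (0.95 × 4 + 0.05) = 3.94 − 3.85 = +0.09
- Failure rates exchanged: −0.09

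**Effect on the Paired − Pre gain.** Take retained means of 4.2 (Paired) and 3.3 (Pre), a restricted gain of 0.90.

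- Pre fails in 5%, Paired in 1%: (0.99 × 4.2 + 0.01) − (0.95 × 3.3 + 0.05) = 4.168 − 3.185 = 0.98
- Pre fails in 1%, Paired in 5%: (0.95 × 4.2 + 0.05) − (0.99 × 3.3 + 0.01) = 4.040 − 3.277 = 0.76

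The direction is therefore fixed for a single level, provided reads scored 1 exist and are removed. It is not fixed for either comparison.

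**The case against.** The strongest reply is that the score-1 rule attaches to a diagnosis of 'not assessable', whereas the Extended sets turn on the assessability of the images. These are two items in two sections, and nothing says that a failed image set must be recorded with that diagnosis. A reader might infer that the protocol scores every failed image set as 1; the text does not go that far. Where the written rule clearly applies, to assessable images that allow no diagnosis, the score of 1 stays in the planned tables. Off-site scores for failed sets may not even exist, since Protocol 8.4.7 has the independent readers assess evaluable images. Entering a 1 where nothing was recorded would be imputation, which SAP 3.5.1 and Protocol 11.4.2 exclude. This stands, and it makes the bias conditional on what readers recorded.

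Nor is it certain that every failed read is removed. If one reader's judgement suffices for the Extended sets, as it does for FAS1 and FAS2, a set that failed for one reader but was usable for another stays in. This stands too.

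A reader might also infer that the Paired − Pre gain is understated, or that an imbalance between agents is hidden. The first holds only if Pre sets fail more often than Paired sets by enough to matter. Injection failure, one of the listed reasons, would affect the post-contrast images and push the other way. The second is contradicted by Tables 14.2.2.18 to 14.2.2.21, which show assessability by agent and modality in the All Randomized Set, and by Listings 16.2.6.13 to 16.2.6.16, which list diagnosis and confidence for the Screened Patients Set.

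Finally, the protocol itself placed secondary criteria in sets defined by assessable images (11.3.2 and 11.3.6), and the Extended sets are wider than the SAP's FAS because they drop the matching-lesion condition. Reporting failures under technical adequacy and confidence among readable examinations is a coherent separation. It still leaves no table of recorded confidence over all examinations performed.

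**Conclusion.** The point holds in a limited form. All planned confidence tables are conditioned on assessable images, and a patient excluded for a failed image set takes the usable set out as well. Where failed images were recorded as diagnosis 'not assessable' with confidence 1, the exclusion depends on the outcome and the tabulated levels are biased upward by f × (m − 1): about 0.03 points at 1% and 0.15 at 5% on the five-point scale, for an assumed retained mean of 4. The documents supply neither f nor m.

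No direction can be claimed for the Paired − Pre gain or the agent difference. Confidence is a secondary criterion summarised without a test, and no primary conclusion depends on it. This is an inexpensive improvement, not a serious defect.

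**What to change.** In SAP 5.6.2 and Tables 14.2.2.46 to 14.2.2.49, tabulate recorded diagnosis and confidence, per reader and modality, in the All Randomized Set:

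- Paired versus Pre: all patients of that set with a gadopiclenol MRI.
- Gadopiclenol versus gadobutrol: all patients of that set with both MRIs performed.

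Repeat the Protocol 7.2.7 rule in SAP 2.2.2 and apply it wherever the recorded diagnosis is 'not assessable'. Show image sets with no recorded score as a separate category, without imputing them. Keep the Extended FAS tables alongside, and state in SAP 5.2 whose judgement of assessability defines those sets.

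The cost is SAP wording and a re-run of four descriptive tables on whatever was recorded. The downside is that failures due to patient movement or the scanner slightly lower the means for both agents.
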